5.2. Number of Participants

Approximately 24 subjects may be enrolled so that at least 18 evaluable subjects complete the study. For purposes of this study, a subject completes the study when all scheduled procedures shown in the Schedule of Activities (Section 2) have been finished.

5.3. End of Study Definition

End of the study is the date of the last visit or last scheduled procedure shown in the Schedule of Activities (Section 2) for the last subject.

5.4. Scientific Rationale for Study Design

Conducting this study in healthy subjects mitigates the potential confounding effects of the disease state and concomitant medications in patients.

An open-label design is required, as subjects and staff administering the injections will be able to distinguish between the SDP and PFS, including number of injections. In order to minimize any potential period-effect, a randomized, 2-sequence, crossover design has been selected. Based on the apparent terminal elimination half-life ($t_{1/2}$) of dulaglutide of approximately 5 days

(Trulicity® USPI 2017), a washout period of at least 28 days between doses is considered sufficient not to impact the PK outcome of the second period.

Pharmacokinetic sampling up to 336 hours is sufficient to generate an evaluable PK profile for dulaglutide. A single dose of dulaglutide will be administered in each period, as this is considered sufficient to evaluate the relative bioavailability of dulaglutide administered via the 2 devices (SDP versus PFS).

5.5. Justification for Dose

The dose selected for this study (4.5 mg) is the highest dose for the Phase 2 study (GBGJ). Based on PK/pharmacodynamic model projections, doses higher than the currently approved 0.75- and 1.5-mg doses that are included in Study GBGJ were identified based on their potential to yield greater HbA1c reductions and weight loss, with an acceptable safety and tolerability profile. Based on predicted plasma exposures in patients with T2D receiving the highest investigational dulaglutide dose of 4.5 mg, the margins of safety (i.e., plasma exposure multiples at the NOAEL) in chronic toxicology studies in monkeys and rats were 162-fold and 55-fold, respectively. Additional details are provided in Section 3.3.

Dulaglutide is approved for SC administration by SDP or PFS (Trulicity® USPI 2017; previously demonstrated to be bioequivalent). Therefore, this study will compare the PK of 2 formulations of dulaglutide administered by these 2 devices. Safety and efficacy data using the commercial formulation and device will also be obtained in the planned Phase 3 trial (Study GBGL).

6. Study Population

Eligibility of subjects for the study will be based on the results of screening medical history, physical examination, vital signs, clinical laboratory tests, and ECG.

The nature of any conditions present at the time of the physical examination and any preexisting conditions will be documented.

Screening may occur up to 27 days prior to enrollment. Subjects who are not enrolled within 27 days of screening may be subjected to an additional medical assessment and/or clinical measurements to confirm their eligibility.

Prospective approval of protocol deviations to recruitment and enrollment criteria, also known as protocol waivers or exemptions, are not permitted.

6.1. Inclusion Criteria

Subjects are eligible for inclusion in the study only if they meet all of the following criteria at screening and/or enrollment:

[1] are overtly healthy males or females, as determined by medical history and physical examination

[1a] male subjects:

- i. Men with partners of childbearing potential, for the duration of the study and for 120 days after the last dose of study drug, will either remain abstinent (if this is their preferred and usual lifestyle) or use at least 1 highly effective (less than 1% failure rate) method of contraception (such as combination oral contraceptives, implanted contraceptives, or intrauterine device) or an effective method of contraception (such as male or female condoms with spermicide, diaphragms with spermicide, or cervical sponges). The subject may choose to use a barrier method of contraception. (Barrier protection methods without concomitant use of a spermicide are not an effective or acceptable method. Thus, each barrier method must include use of a spermicide. It should be noted, however, that the use of male and female condoms as a double barrier method is not considered acceptable due to the high failure rate when these barrier methods are combined.)
- ii. Men should refrain from sperm donation for the duration of the study and for 120 days after the last dose of study drug
- iii. Men who are in exclusively same sex relationships (when it is their preferred and usual lifestyle) are not required to use contraception

[1b] female subjects:

- i. Women of childbearing potential who are abstinent (if this is complete abstinence, as their preferred and usual lifestyle) or in a same sex relationship (as part of their preferred and usual lifestyle) must agree to either remain abstinent or stay in a same sex relationship without sexual relationships with males
- ii. Otherwise, women of childbearing potential participating must agree to use one highly effective method (less than 1% failure rate) of contraception, or a combination of 2 effective methods of contraception for the entirety of the study
 - a. Women of childbearing potential must test negative for pregnancy prior to initiation of treatment as indicated by a negative serum pregnancy test at the screening visit followed by a negative urine pregnancy test within 24 hours prior to exposure
 - b. Either 1 highly effective method of contraception (such as combination oral contraceptives, implanted contraceptives, or intrauterine device) or a combination of 2 effective methods of contraception (such as male or female condoms with spermicide, diaphragms with spermicide, or cervical sponges) will be used. The subject may choose to use a double barrier method of contraception. Barrier protection methods without concomitant use of a spermicide are not a reliable or acceptable method. Thus, each barrier method must include use of a spermicide. It should be noted that the use of male and female condoms as a double barrier method is not considered acceptable due to the high failure rate when these methods are combined
- iii. Women not of childbearing potential may participate and include those who are:
 - a. infertile due to surgical sterilization (hysterectomy, bilateral oophorectomy, or tubal ligation) or congenital anomaly such as Mullerian agenesis; or
 - b. post-menopausal – defined as
 - i. A woman at least 50 years of age with an intact uterus, not on hormone therapy, who has had either
 1. cessation of menses for at least 1 year, or
 2. at least 6 months of spontaneous amenorrhea with a follicle-stimulating hormone >40 mIU/mL; or

- ii. A woman 55 years or older not on hormone therapy, who has had at least 6 months of spontaneous amenorrhea; or
 - iii. A woman at least 55 years of age with a diagnosis of menopause prior to starting hormone replacement therapy
- [2] are at least 18 years old
 - [3] have a body mass index (BMI) ≥ 23 kg/m²
 - [4] have clinical laboratory test results within normal reference range for the population or investigative site, or results with acceptable deviations that are judged to be not clinically significant by the investigator
 - [5] have venous access sufficient to allow for blood sampling as per the protocol
 - [6] are reliable and willing to make themselves available for the duration of the study and are willing to follow study procedures
 - [7] are able and willing to give signed informed consent

6.2. Exclusion Criteria

Subjects will be excluded from study enrollment if they meet any of the following criteria at screening and/or enrollment:

- [8] are investigative site personnel directly affiliated with this study and their immediate families. Immediate family is defined as a spouse, biological or legal guardian, child, or sibling
- [9] are Lilly employees or are employees of a third-party involved in the study who require exclusion of their employees
- [10] are currently enrolled in a clinical study involving an investigational product or any other type of medical research judged not to be scientifically or medically compatible with this study
- [11] have participated, within the last 30 days, in a clinical study involving an investigational product. If the previous investigational product has a long half-life, 5 half-lives or 30 days (whichever is longer) should have passed
- [12] have previously completed or withdrawn from this study or any other study investigating dulaglutide within 3 months prior to screening
- [13] have known allergies to GLP-1-related compounds including dulaglutide, any components of the formulation, or history of significant atopy
- [14] have an abnormality in the 12-lead ECG that, in the opinion of the investigator, increases the risks associated with participating in the study

- [15] have an abnormal blood pressure and/or pulse rate as determined by the investigator
- [16] have a history or presence of cardiovascular, respiratory, hepatic, renal, endocrine, hematological, or neurological disorders capable of significantly altering the absorption, metabolism, or elimination of drugs; of constituting a risk when taking the investigational product; or of interfering with the interpretation of data
- [17] have a history or presence of pancreatitis (history of chronic pancreatitis or idiopathic acute pancreatitis) or gastrointestinal disorder (e.g., relevant esophageal reflux or gall bladder disease) or any gastrointestinal disease which impacts gastric emptying (e.g., gastric bypass surgery, pyloric stenosis, with the exception of appendectomy) or could be aggravated by GLP-1 analogs. Subjects with dyslipidemia and subjects who had cholecystolithiasis (removal of gall stones) and/or cholecystectomy (removal of gall bladder) in the past, with no further sequelae, may be included in the study at the discretion of the screening physician
- [18] have family history of medullary thyroid cancer (MTC) or a genetic condition that predisposes to MTC
- [19] have known or ongoing psychiatric disorders considered clinically significant in the opinion of the investigator
- [20] regularly use known drugs of abuse and/or show positive findings on drug screening
- [21] show evidence of human immunodeficiency virus (HIV) infection and/or positive HIV antibodies
- [22] show evidence of hepatitis C and/or positive hepatitis C antibody
- [23] show evidence of hepatitis B and/or positive hepatitis B surface antigen
- [24] are women who are pregnant or lactating
- [25] have donated blood of more than 500 mL within 4 weeks prior to screening
- [26] have used or intend to use over-the-counter medication other than acetaminophen within 7 days prior to dosing or prescription medication (with the exception of vitamin/mineral supplements and/or hormone replacement therapy [HRT]) within 14 days prior to dosing
- [27] have an average weekly alcohol intake that exceeds 21 units per week (males up to age 65) or 14 units per week (males over 65 and females), are unwilling to stop alcohol consumption from at least 48 hours prior to Check-in (Day -1) until discharge from the CRU in each period, or are unwilling to limit intake to a maximum of 2 units per day on all other days from screening through follow-up

(1 unit = 12 oz or 360 mL of beer; 5 oz or 150 mL of wine; 1.5 oz or 45 mL of distilled spirits)

- [28] smoke more than 10 cigarettes (or equivalent in nicotine) per day, and are unwilling to refrain from smoking on the day of dulaglutide administration or are unable to abide by CRU restrictions
- [29] in the opinion of the investigator or sponsor, are unsuitable for inclusion in the study

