7.7. Concomitant Therapy

With the exception of vitamin/mineral supplements and/or HRT, prescription medications are not to be taken from 14 days prior to drug administration and throughout the study.

Over-the-counter medications other than acetaminophen are not to be taken from 7 days prior to drug administration and throughout the study. The use of topical medication may be permitted if no evidence of chronic dosing with the risk of systemic absorption exists.

In general, concomitant medication should be avoided; however, acetaminophen (1 g, maximum 4 g per 24 hours) may be administered at the discretion of the investigator for treatment of headaches, etc. If the need for concomitant medication (other than acetaminophen) arises, inclusion or continuation of the subject may be at the discretion of the investigator after consultation with a Lilly Clinical Pharmacologist (CP) or Clinical Research Physician (CRP). Any medication used during the course of the study must be documented.

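### Does the medication ban in exclusion [26] and Section 7.7 undo the contraceptive methods that inclusion [1b] accepts?

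*Protocol*

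**What the plan says.** Criterion [1b] ii in Protocol Section 6.1 applies to women of childbearing potential who are not abstinent or in a same-sex relationship. It asks for one highly effective method or "a combination of 2 effective methods of contraception for the entirety of the study". Item b gives examples: "Either 1 highly effective method of contraception (such as combination oral contraceptives, implanted contraceptives, or intrauterine device", or two effective methods such as condoms, diaphragms or sponges. Each barrier method has to be used with a spermicide.

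Criterion [26] in Section 6.2 excludes subjects who "have used or intend to use over-the-counter medication other than acetaminophen within 7 days prior to dosing", and also those who use "prescription medication (with the exception of vitamin/mineral supplements and/or hormone replacement therapy [HRT]) within 14 days prior to dosing".

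Section 7.7 extends both restrictions beyond entry. Apart from supplements and HRT, "prescription medications are not to be taken from 14 days prior to drug administration and throughout the study". It adds two relaxations that [26] lacks:

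- "The use of topical medication may be permitted if no evidence of chronic dosing with the risk of systemic absorption exists".
- If a need for other medication arises, "inclusion or continuation of the subject may be at the discretion of the investigator after consultation with a Lilly Clinical Pharmacologist (CP" or the sponsor's research physician.

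The opening of Section 6 says that prospective approvals of deviations from enrollment criteria, "also known as protocol waivers or exemptions, are not permitted".

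The SAP does not take up the point. Its Section 9.4.2 codes and lists concomitant medication, and its Section 8 considers all protocol deviations when subjects are assigned to populations.

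**The concern.** One criterion offers a woman a method and another appears to exclude her for using it. The exemptions in [26] are specific (supplements, HRT and acetaminophen), which makes the silence on contraceptives look deliberate. HRT does not obviously fill the gap, because the inclusion criteria otherwise refer to hormone therapy only when defining post-menopausal women.

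Two outcomes seem possible:

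- A site that applies [26] to the letter records a screen failure, and Section 6.4 does not allow re-screening.
- A site that follows [1b] enrolls her. She may later be judged not to have met enrollment criteria, which brings in the sponsor discussion and documented approval of Section 8.1.1 and the deviation review of SAP Section 8.

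At stake would be inconsistent eligibility decisions and, if women were then removed from the pharmacokinetic population, some loss of data.

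**Working it through.** No figure in the plan depends on this point, so there is nothing to reproduce. The check compares the texts and then follows each reading through to the analysis.

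**Step 1: is there a clash?**

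| Product | [1b] | [26] | Section 7.7 |
|---|---|---|---|
| Combination oral contraceptive | Named as accepted | No exemption | No exemption; case-by-case discretion |
| Implanted contraceptive | Named as accepted | No exemption | No exemption; case-by-case discretion |
| Spermicide with a barrier method | Required | No exemption | Possibly the topical allowance |

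The clash needs one assumption that the documents do not state: that these products are prescription or over-the-counter medication in the sense of [26]. Both classes are restricted, so it does not matter which applies. On that assumption the clash follows from the text. Applied evenly, it also reaches spermicide, so users of barrier methods are not clearly outside it.

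**Step 2: does an existing clause settle it?** Not fully. The discretion clause in Section 7.7 mentions inclusion as well as continuation, so it does reach entry. But it is framed around a need that arises, and it stands beside the ban on waivers in Section 6. Whether it covers a method already in use at entry is left to interpretation.

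**Step 3: consequence if [26] is applied literally.** Affected women fail screening and are not randomized. Men, women not of childbearing potential, and women who meet [1b] without a medicated product remain eligible. Section 10.1 plans about 24 enrolled so that at least 18 complete, and lets randomized subjects be replaced to reach that number. The precision statement in that section rests on 18 subjects and a within-subject coefficient of variation of 21%. Neither input depends on which contraceptive methods are admitted at screening.

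**Step 4: consequence if [1b] governs.** Affected women are enrolled and their medication is documented and listed. Section 10.3.2.2 and SAP Section 9.3.2 fit treatment, period and sequence with a random subject effect, so the pen-to-syringe contrast is formed within subject. A factor present in both periods cancels from that contrast. [1b] asks for contraception throughout, so such use would normally be present in both periods. A change of method between periods would not be tied to device, because the order of devices is randomized. If deviation review under SAP Section 8 removed such a woman entirely, both her periods would go together, and the remaining contrasts would still be within subject.

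**Step 5: subject protection.** Under either reading, no woman of childbearing potential enters without meeting [1b]. The literal reading keeps some women out; it does not leave an enrolled woman with less contraception than [1b] demands. Pregnancy testing at screening, on Day -1 of each period and at follow-up is the same either way.

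**The case for a change.** The strongest case for a change is that the text gives a careful site real grounds for either reading. Section 6.2.1 says that criteria [10] through [29] exclude, among other things, concomitant medication use that may confound the endpoints. The literal reading is therefore not perverse, and a screen failure under it is final. One sentence would remove the doubt, at no cost to sample size, pharmacokinetic analysis or SAP.

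Most of that stands as a comment on drafting. The wording is incomplete and the sponsor's clinical team could tidy it. It does not show that a result would come out differently. The argument that an inconsistency must endanger the study also meets a difficulty of its own. Taken to its end, the literal reading would reach spermicide as well and would empty much of what [1b] requires. This suggests a gap in drafting more than a deliberate rule, though the documents do not confirm it. The procedures for uncertain cases already exist: sponsor consultation in Section 7.7, documented approval in Section 8.1.1 and deviation review in SAP Section 8.

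**Conclusion.** The inconsistency between [1b], [26] and Section 7.7 is real on the assumption that contraceptives count as medication. It is a missing detail in eligibility wording. The passages have to be read together and reconciled by the sponsor's clinical team, and this review takes no view on which rule should stand.

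No change to the design or analysis follows. The size is nil for the geometric mean ratios and their 90% confidence intervals, for the target of at least 18 completers, and for the descriptive safety summaries. The number of women concerned is not stated and cannot be derived from the documents. The conclusion rests on three things: the within-subject comparison, replacement of subjects up to the completion target, and [1b] binding every enrolled woman of childbearing potential under either reading.

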6.2.1. Rationale for Exclusion of Certain Study Candidates

Criteria [8] and [9] prevent conflict of interest in study participants. Criteria [10] through [29] exclude medical conditions, medication intolerance, concomitant medication use, and other items that may confound the assessment of study endpoints.

6.3. Lifestyle and/or Dietary Requirements

Throughout the study, subjects may undergo medical assessments and review of compliance with requirements before continuing in the study.

6.3.1. Meals and Dietary Restrictions

Prior to dulaglutide dosing (Day 1 of Periods 1 and 2), subjects will be fasted for approximately 8 hours and a standard breakfast will be provided approximately 15 minutes after dosing.

6.3.2. Caffeine, Alcohol, and Tobacco

No alcohol will be allowed from at least 48 hours prior to admission (Day -1) until discharge, and alcohol intake will be limited to a maximum of 2 units/day on all other days from screening through the follow-up visit (1 unit = 12 oz or 360 mL of beer; 5 oz or 150 mL of wine; 1.5 oz or 45 mL of distilled spirits).

Subjects will be questioned about their smoking habits at screening. Smoking will not be permitted on dosing days and subjects will abide by CRU restrictions.

6.3.3. Activity

Subjects should not undertake unaccustomed vigorous or prolonged exercise from screening through the post study follow-up visit.

6.4. Screen Failures

Individuals who do not meet the criteria for participation in this study (screen failure) may not be re-screened.

7. Treatment

7.1. Treatment Administered

On Day 1 of each period, subjects will receive a single dose of 4.5 mg dulaglutide administered SC as a single SDP injection or as 3 injections by PFS according to the randomization schedule. There will be a minimum 28-day washout period between doses. [Table GBGM.2](#) shows the treatment regimens.

Doses will be administered into the SC tissue of the abdominal wall. A separate Instructions for Use document will be provided by Lilly. Where possible, the same member of staff should administer the injections to all subjects. Prior to dulaglutide dosing, subjects will be fasted for approximately 8 hours and a standard breakfast will be provided approximately 15 minutes after dosing.

Table GBGM.2. Treatments Administered

| Treatment Name | LY2189265 | LY2189265 |
|------------------------------|---------------------------------|--|
| Formulation and Presentation | Solution in a prefilled syringe | Solution in a single dose pen ^a |
| Dose | 3 x 1.5 mg (4.5 mg total dose) | 1 x 4.5 mg (4.5 mg total dose) |
| Concentration | 3.0 mg/mL | 9.0 mg/mL |
| Volume per Injection | 0.5 mL | 0.5 mL |
| Number of Injections | 3 | 1 |
| Dosing Instructions | SC injection in abdomen | SC injection in abdomen |

Abbreviations: SC = subcutaneous.

^a Increased polysorbate 80 content to accommodate higher dulaglutide content.

The investigator or designee is responsible for:

- explaining the correct use of the investigational product(s) to the site personnel
- verifying that instructions are followed properly
- maintaining accurate records of investigational product dispensing and collection
- returning all unused medication to Lilly or its designee at the end of the study

Note: In some cases, sites may destroy the material if, during the investigative site selection, the evaluator has verified and documented that the site has appropriate facilities and written procedures to dispose of clinical materials.

